### 1.2. Secondary Objectives

A. All cohorts: Calculate the incidence of reported CTCAE v 4.03 adverse events and abnormal laboratory test results

B. All cohorts: Estimate the overall response rate (ORR) per RECIST version 1.1, time to tumor progression (TTP), PFS at 8 weeks and 16 weeks, overall survival (OS), disease-specific survival (DSS)

C. Cohorts A and B, after crossover: Assess PFS, RR, TTP, OS, and DSS following administration of regorafenib in the open label portion of the study.

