## 6.4 Hypertension

Hypertension is a recognized AE associated with regorafenib treatment. Subject will have their blood pressure measured at least weekly at the study site on weeks 1, 2, 3, 5, and 7. If additional blood pressure measurements are done outside the study site, and the blood pressure is > 140 mm Hg systolic or > 90 mm Hg diastolic (NCI CTCAE v 4.03), then the subject must contact study personnel. The management of hypertension, including the choice of antihypertensive medication, will be performed according to local standards and to the usual practice of the investigator. Every effort should be made to control blood pressure by medical means other than study drug dose modification. If necessary, **Table 6.5** below outlines suggested dose reductions.

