**Table 6.4.2 Management of Treatment Emergent Hypertension for pediatric patients**

**Please refer to appendix:**

Grade (CTCAE v 4.03)	Antihypertensive Therapy	Regorafenib or placebo Dosing
Grade 1 If age ≤ 17 years: Asymptomatic, transient (< 24 hrs) BP increase > ULN; intervention not indicated. If age > 17	Consider increased BP monitoring; start anti-hypertensive medication if appropriate	No modification

years: (SBP 120-139 mmHg or DBP 80-89 mmHg)		
Grade 2 asymptomatic If age ≤ 17 years: Recurrent or persistent (≥ 24 hrs) BP > ULN; If age > 17 years: (SBP 140-159 mmHg or DBP 90-99 mmHg)	-If age ≤ 17 years: monotherapy indicated, -If age > 17 years: As in Table 6.5	Continue Study drug
Grade 2 symptomatic OR Grade 3: (> 17 years: SBP > 160 mmHg or DBP > 100 mmHg) requiring more than one drug or more intensive therapy than previously (all ages)	• Start or adjust anti-hypertensive medication as in table 6.5	• Hold study drug until symptoms resolve AND BP < 95th percentile ULN for age, height, and gender, if age ≤ 17 years; or BP < 160/90 mmHg if age > 17 years. Resume study at 100% (full) dose. If similar toxicity recurs, discontinue study drug.
Grade 4 (all ages) life threatening (eg, hypertensive crisis or malignant hypertension)	Per institutional guidelines	Discontinue study drug

**90th and 95th PERCENTILE BLOOD PRESSURE BY PERCENTILE HEIGHT IN  
GIRLS AGE 1-17 YEARS**

Age (Year)	BP Percentile	Systolic BP (mmHg)							Diastolic BP (mmHg)						
		Percentile of Height							Percentile of Height						
↓		5th	10th	25th	50th	75th	90th	95th	5th	10th	25th	50th	75th	90th	95th
1	90th	97	97	98	100	101	102	103	52	53	53	54	55	55	56
	95th	100	101	102	104	105	106	107	56	57	57	58	59	59	60
2	90th	98	99	100	101	103	104	105	57	58	58	59	60	61	61
	95th	102	103	104	105	107	108	109	61	62	62	63	64	65	65
3	90th	100	100	102	103	104	106	106	61	62	62	63	64	64	65

	95th	104	104	105	107	108	109	110	65	66	66	67	68	68	69
4	90th	101	102	103	104	106	107	108	64	64	65	66	67	67	68
	95th	105	106	107	108	110	111	112	68	68	69	70	71	71	72
5	90th	103	103	105	106	107	109	109	66	67	67	68	69	69	70
	95th	107	107	108	110	111	112	113	70	71	71	72	73	73	74
6	90th	104	105	106	108	109	110	111	68	68	69	70	70	71	72
	95th	108	109	110	111	113	114	115	72	72	73	74	74	75	76
7	90th	106	107	108	109	111	112	113	69	70	70	71	72	72	73
	95th	110	111	112	113	115	116	116	73	74	74	75	76	76	77
8	90th	108	109	110	111	113	114	114	71	71	71	72	73	74	74

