## **7. ADVERSE EVENTS: LIST AND REPORTING REQUIREMENTS**

Adverse event (AE) monitoring and reporting is a routine part of every clinical trial. The following list of AEs (Section 7.1) and the characteristics of an observed AE (Section 7.2) will determine whether the event requires expedited reporting **in addition** to routine reporting. For routine reporting it is expected that all adverse events grade 3 or greater are recorded.

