#### **12.1.2 Safety variables**

A treatment-associated adverse event (TAAE) is defined as an AE that was not present at baseline, or an exacerbation of a pre-existing AE. For laboratory data, a treatment-associated abnormal laboratory value (TAAV) represents an abnormal value that was normal at baseline.

Safety variables of analysis include the following:

- Proportions of patients with any TAAEs
- Proportions of patients with serious TAAEs
- Proportions of patients with Grade 3 or greater TAAEs
- Proportions of patients with severe TAAE
- Proportions of patients with TAAEs leading to study drug discontinuation
- Proportions of patients with TAAEs leading to dose modifications
- Proportions of patients with drug-related TAAEs
- Proportions of patients with TAAVs
- Mean and median changes from baseline in vital signs
- Mean and median changes from baseline in clinical laboratory measures
- Mean and median changes from baseline in measures from electrocardiography.

It is noted that patients who cross over from placebo to receive open-label regorafenib will have treatment-related derivations from first dose of placebo during the double-blind period and treatment-related derivations from first dose of regorafenib during the open-label portion of the study.

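### The planned blood-pressure summaries cannot show how many children cross their age, sex and height limit, and asymptomatic Grade 1-2 hypertension in children may not be reported

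*Combined protocol and SAP*

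**What the plan says.** Section 12.1.2 (Safety variables) lists one analysis of blood pressure as a measurement: "Mean and median changes from baseline in vital signs". It gives no count above a limit, no change of category, no percentile and no grouping by age.

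The same list has proportions that hypertension could enter as a treatment-associated adverse event (TAAE): "Proportions of patients with any TAAEs", "Proportions of patients with drug-related TAAEs" and "Proportions of patients with TAAEs leading to dose modifications", besides serious events, Grade 3 or greater events and events leading to discontinuation. The matching secondary objective in section 1.2 is to "Calculate the incidence of reported CTCAE v 4.03 adverse events and abnormal laboratory test results", so it depends on what sites report.

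On reporting, section 7 states: "For routine reporting it is expected that all adverse events grade 3 or greater are recorded". Sections 7.1.1.3 and 7.2.1 use the same threshold. Section 7.1.2 asks for the final outcome of each adverse event on the CRF and names no grade there.

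Section 6.4 states: "Hypertension is a recognized AE associated with regorafenib treatment". Table 6.4.2 grades it at age 17 or under against an upper limit of normal. An asymptomatic rise lasting under 24 hours is Grade 1, a recurrent or lasting rise is Grade 2, and needing more than one drug or more intensive therapy is Grade 3. Its blood-pressure condition for ending a hold at that age is "BP < 95th percentile ULN for age, height, and gender, if age ≤ 17 years", and tables of the 90th and 95th percentiles by age, sex and height follow. Section 3.1.1 admits patients from age 5 to Cohort D and from age 10 to the other cohorts.

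**The concern.** The synopsis names hypertension among the specific safety concerns. The protocol uses a percentile standard for children in eligibility (3.2.10) and in management (Table 6.4.2), but the analysis section does not carry it over. A mean or a median describes the centre of the changes. The safety question for children is how many moved above their own limit, and a centre does not answer that.

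Laboratory values are treated better. Section 12.1.2 counts patients whose value was normal at baseline and abnormal later. Section 7.1.3 puts a treatment-emergent laboratory abnormality on the adverse event eCRF if it requires a change in concomitant therapy, whatever its grade. Blood pressure has neither rule.

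Treatment also works against the summary. Table 6.4.2 allows an antihypertensive at Grade 1 and indicates monotherapy at asymptomatic Grade 2, and both would bring later readings back toward baseline. At stake is how complete the safety account is for patients under 18, whom section 2.5 describes as newly able to be dosed.

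**Working it through.** The documents give no figure for blood pressure (no expected rate, precision or sample size), so there is none to reproduce. Four checks follow.

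**1. The protocol's own limits.** Systolic values in mm Hg at the 50th height percentile, from the section 6.4 tables:

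| Age, sex | 90th | 95th | Gap | 95th minus 120 (adult Grade 1 starts) | 140 (adult Grade 2 starts) minus 95th |
|---|---|---|---|---|---|
| 5, girl | 106 | 110 | 4 | -10 | 30 |
| 5, boy | 108 | 112 | 4 | -8 | 28 |
| 10, girl or boy | 115 | 119 | 4 | -1 | 21 |
| 17, girl | 125 | 129 | 4 | 9 | 11 |
| 17, boy | 132 | 136 | 4 | 16 | 4 |

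The limit spans 136 - 110 = 26 mm Hg. A 5-year-old can pass it while 8 to 10 mm Hg below the adult Grade 1 boundary.

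**2. A change alone does not tell whether the limit was crossed.** For a girl aged 6 of median height the 95th percentile is 111. A rise of 12 from 100 gives 112, above it. A larger rise of 20 from 90 gives 110, below it.

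**3. Mean and median do not fix the count.** Take 12 patients, the approximate size of Cohort D. Let k rise by D mm Hg and the rest not change (k and D are assumptions). Then mean = kD/12. The median is 0 for k up to 5 and D for k of 7 or more.

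| k | D | Mean | Median |
|---|---|---|---|
| 1 | 15 | 15/12 = 1.25 | 0 |
| 3 | 5 | 15/12 = 1.25 | 0 |
| 2 | 15 | 30/12 = 2.5 | 0 |
| 3 | 10 | 30/12 = 2.5 | 0 |
| 9 | 10 | 90/12 = 7.5 | 10 |

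Suppose the patients who rise are children of median height starting at their 90th percentile. The gap is 4 mm Hg at the ages tabulated, so a rise of 5 crosses the limit. Rows one and two then have one and three children crossing, with identical summaries. The last row shows that a rise in most patients does move both summaries.

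Precision adds to this. With an assumed SD of change of 8 to 12 mm Hg, the 95% half-width for a mean of 12 is 2.201 × SD/√12, that is 5.08 to 7.62 mm Hg. Means of 1.25 or 2.5 lie well inside it.

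**4. Routes into the results at age 17 or under,** reading Table 6.4.2 against sections 7 and 12.1.2:

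| Event | Drug action in Table 6.4.2 | Must be reported? | Route into results |
|---|---|---|---|
| Grade 1 (asymptomatic) | None | No | None assured |
| Grade 2, asymptomatic | Continue | No | None assured |
| Grade 2, symptomatic | Hold; discontinue if it recurs | Not by grade | TAAE leading to dose modification or discontinuation, if the site records it |
| Grade 3 or worse | Hold or discontinue | Yes | Assured |

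The proportions with any or with drug-related TAAEs would not reveal the first two rows even if sites recorded them. In the pediatric phase I trial (2.4.3), 41 of 41 treated subjects had at least one event and 40 of 41 (97.6%) a drug-related one, so such proportions sit near their ceiling with or without hypertension. Section 11.1.3 does not list hypertension among the events of special safety interest.

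**The case against.** The best defence is that change from baseline is a within-patient measure. It already removes the difference in starting level between a child and an adult, so a common rise would appear. That stands, and the gap is limited to rises in a minority.

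Nor do the documents bar recording below Grade 3. Section 7.1.1.3 grades all events 1 to 5 and asks for detail from Grade 3, and section 7.1.2 wants the outcome of each event. This also stands: the lower-grade route is open but not assured.

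Three stronger readings are tempting, and the documents do not support them.

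- A reader might infer that readings will be pooled from age 5 to adult. Section 12.1.2 is silent on age. The combined analysis of Cohort D in section 12.2 concerns histology, and ages 5 to 9 can occur only in that cohort.
- A reader might infer that hypertension below Grade 3 in children will not show at all. A rise in most patients would show, and so would symptomatic Grade 2 events recorded as leading to dose modification.
- A reader might infer from section 2.4.3 that hypertension is an established main harm in children at this trial's dose. The dose-limiting hypertension there was at 93 mg/m², while the pediatric starting dose here is 82 mg/m². Hypertension is absent from the drug-related events listed at 20% or more and from the drug-related Grade 3 or worse events listed at 5% or more. I therefore attach no expected incidence.

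Finally, one reading above the 95th percentile is not Grade 2 under Table 6.4.2, which requires recurrence or persistence. A bare count of any high reading would mix grades and include elevation present before treatment, so the fix has to guard against both.

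**Conclusion.** The point holds as a gap in safety reporting. The planned blood-pressure summaries cannot yield the number of children who cross their limit, and asymptomatic Grade 1-2 hypertension at age 17 or under has no assured route into the results. How many children this affects cannot be stated, because the documents give neither the number under 18 nor an expected rate. The 12-patient examples use assumed rises and starting values and show only that different counts can share one mean and median.

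The conclusion assumes that section 12.1.2 lists everything planned for measured blood pressure, that sites apply the Grade 3 rule as written, and that some patients are under 18. The primary endpoint, the sample sizes and the decision rules are unaffected. The change is worth making because it is cheap and concerns a harm that the protocol itself names.

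**What to change.** In section 12.1.2 add, separately for under-18s and adults:

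- The proportion of patients at or below the protocol's own limit at baseline who exceed it on treatment. The limit is the 95th percentile for age, sex and height at age 17 or under and otherwise the CTCAE mm Hg limits, with the grade boundary named. Show single and repeated exceedances separately.
- The maximum on-treatment change, for children also relative to the section 6.4 tables.
- Worst grade, counting new or increased antihypertensives, only if concomitant medications are captured in the eCRF. Section 5.5 places them in source documentation and section 4.1 restricts what the eCRF holds, so this must be confirmed first.

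Keep mean and median change as descriptive. Reconcile the proportion with any TAAE in section 12.1.2 with sections 7, 7.1.1.3, 7.1.2 and 7.2.1: either lower-grade events are recorded, or the proportion is labelled as covering Grade 3 or worse.

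The cost is SAP wording and a small derivation. Screening height (9.1), visit vital signs (9.2), age and sex are already collected. The SAP should also name the source for converting height to a percentile, since I find none in the documents. The worst-grade item may need an eCRF change. The counts will be small and descriptive, and no clinical management rule changes.

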## **12.2 Study Design/Endpoints**

### **Cohorts A and B (liposarcoma and osteosarcoma)**

Each of cohorts A and B will be studied using a randomized placebo controlled phase II design with a progression free survival endpoint. Outcomes will be determined on an intention to treat analysis.

Each cohort substudy will be powered to detect a difference of at least 3 months in median PFS, which has been discussed among expert sarcoma oncologists as a clinically meaningful difference in outcome. This corresponds to a median control group PFS of 2 months, median treatment group PFS of 5 months, and hazard ratio of 0.4 for treatment/control groups.

42 events are needed to detect a targeted difference with 90% power and 5% one-sided significance level. The final analysis of the primary PFS endpoint will be conducted when at least 42 patients had disease worsening. 48 eligible patients are expected to be randomized, to achieve the 42 expected events with an enrollment rate of 4 eligible patients per month per substudy. With the predicted accrual rate and PFS parameters, the 42 events are expected to occur in 16 months.

We will limit to a maximum of 16 patients per substudy A & B with WHO performance status of 2. There is no such limitation for substudy C.

Survival will be estimated by the Kaplan-Meier method. The treatment groups will be compared with a one-sided stratified log rank test. All analyses will be done in the intention-to-treat population.

We will conduct a prognostic factor analysis for PFS using a univariate Cox model; significant factors subsequently will be included in a multivariable Cox regression model (cutoff  $p < 0.05$ ). For a predictive analysis of PFS, Cox models will be generated with the investigated factor, treatment, and their interaction, with a significance value of  $p < 0.05$ . P-values will not be adjusted for multiple comparisons.

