### **Trial Design**

We seek to conduct parallel clinical trials of regorafenib in five different metastatic/local-regionally recurrent STBS populations: (A) liposarcoma (pure well-differentiated liposarcoma is excluded); (B) osteogenic sarcoma; (C) Ewing/Ewing-like sarcoma; (D) fusion-positive alveolar rhabdomyosarcoma, embryonal rhabdomyosarcoma and fusion negative alveolar rhabdomyosarcoma; and (E) mesenchymal chondrosarcoma.

For cohorts A and B, we will conduct parallel randomized phase II studies. Patients will be randomized 1:1 between regorafenib and placebo, and followed for disease progression. For those patients with progression of disease on placebo, crossover to active drug will be offered to patients if they remain eligible for the clinical trial in all other respects.

Patients will be further stratified by number of prior lines of therapy (1 vs 2 or more), as well as WHO performance status (0-1 vs 2).

Since PFS with active therapy was very short in advanced Ewing/Ewing-like sarcoma using an IGF1R inhibitor, for example, a single cohort phase II clinical design will be used for cohort C to obtain initial clinical experience with this very aggressive sarcoma subtype.

For cohorts D & E, we will conduct single cohort phase II clinical designs to obtain initial clinical experience with these sarcoma subtypes in patients at least 5 years of age.

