## **12.4 Stratification Factors**

Patients will be stratified by WHO performance status ([0 or 1] vs 2) and by number of prior lines of therapy (1 vs 2 or more). No more than 1/3 of patients will be permitted on cohorts A and B with WHO performance status 2.

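### The univariate prognostic screen for PFS in Cohorts A and B leaves out randomized treatment; if the design HR of 0.4 holds, this shrinks factor effects and costs up to about 10 points of power

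*Combined protocol and SAP*

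**What the plan says.** Section 12.2 (Cohorts A and B) plans a two-step prognostic analysis. Step one: "We will conduct a prognostic factor analysis for PFS using a univariate Cox model". Step two: a multivariable Cox model of the factors that were significant, with a cutoff of p<0.05. Treatment is mentioned in neither step. The next sentence does name treatment, but only for the predictive models, which contain the factor, treatment and their interaction. There is no multiplicity adjustment for these p-values.

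The section does not list the candidate factors, and gives no factor hazard ratio and no power for these models. Section 12.4 names two stratification factors, WHO performance status and number of prior lines. Section 12.2 caps performance status 2 at 16 patients per cohort, which is 16/48 = 1/3.

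The design assumptions are a "median control group PFS of 2 months, median treatment group PFS of 5 months" and a "hazard ratio of 0.4 for treatment/control groups". Of events it says "42 events are needed to detect a targeted difference with 90% power and 5% one-sided significance level", and of size "48 eligible patients are expected to be randomized". The primary comparison is a separate one-sided stratified log-rank test.

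**The concern.** In a Cox model, leaving out a covariate with a strong effect moves the other hazard ratios toward 1, even when that covariate is balanced across the levels of the factor. Randomization does not prevent this. In a cohort of 48 with both arms pooled, treatment at the design effect would be such a covariate, and its value is recorded for every patient.

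The p<0.05 screen is a hard gate. A real factor that fails because its estimate was shrunk is not recovered in the multivariable step. At stake are the list of prognostic factors and the size of their reported hazard ratios. The trial's main conclusion is not at stake.

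**Working it through.** **Inputs from the protocol (Synopsis and Section 12.2).** 48 patients per cohort; "Patients will be randomized 1:1 between regorafenib and placebo"; control median PFS 2 months, treatment median 5 months, so HR = 2/5 = 0.4; 42 events; accrual "with an enrollment rate of 4 eligible patients per month per substudy", so 48/4 = 12 months.

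**Assumptions not in the documents.** The factor's hazard ratio and its prevalence (apart from the 1/3 ceiling for performance status 2); exponential PFS; a factor independent of treatment; a two-sided Wald test at 0.05.

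**Step 1: the plan's own figure.** Schoenfeld's formula with 1:1 allocation:

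d = (z₀.₉₅ + z₀.₉₀)² / (0.25 × (ln 0.4)²) = (1.645 + 1.282)² / (0.25 × 0.840) ≈ 40.8, so 41 events.

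Power at 42 events: √(42 × 0.25) × |ln 0.4| = 3.240 × 0.916 = 2.969; Φ(2.969 − 1.645) = 0.907. The stated 42 events and 90% power reproduce.

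**Step 2: simulation.** 20,000 trials per scenario, uniform 12-month accrual, data cut at the 42nd event. Two Cox models were fitted to each trial: the factor alone, and the factor plus treatment. The table gives binary factors at treatment HR 0.4.

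| Prevalence | True factor HR | Median estimate, alone | Median estimate, with treatment | Power, alone | Power, with treatment | Gain (points) |
|---|---|---|---|---|---|---|
| 50% | 1.5 | 1.42 | 1.51 | 20.0% | 24.4% | 4.4 |
| 50% | 2.0 | 1.84 | 2.04 | 47.9% | 57.7% | 9.8 |
| 50% | 2.25 | 2.04 | 2.30 | 60.2% | 70.6% | 10.4 |
| 50% | 2.5 | 2.25 | 2.59 | 71.6% | 80.6% | 9.0 |
| 50% | 3 | 2.65 | 3.09 | 85.3% | 92.0% | 6.7 |
| 50% | 4 | 3.44 | 4.18 | 96.4% | 98.7% | 2.2 |
| 1/3 | 2.0 | 1.85 | 2.05 | 46.2% | 55.7% | 9.5 |
| 1/3 | 2.5 | 2.27 | 2.58 | 68.9% | 78.7% | 9.8 |
| 25% | 2.0 | 1.89 | 2.08 | 43.4% | 50.8% | 7.5 |
| 25% | 2.5 | 2.30 | 2.60 | 63.9% | 73.1% | 9.2 |

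Gains are taken from unrounded results. At 25% prevalence the gain is 3.2 points at HR 1.5 and 3.8 at HR 4. For a continuous factor it is 9.4 points at HR 1.5 per SD (58.8% to 68.1%) and 2.6 at HR 2.0 per SD. Over all non-null scenarios tried at treatment HR 0.4, the gain runs from 0.4 to 10.4 points. Repeat runs moved individual gains by up to about one point. The adjusted medians sit slightly above the true values, a small-sample effect, but nearer to them than the unadjusted ones at prevalence 1/3 and 1/2.

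**Step 3: false positives.** With a null factor the rejection rate is 4.9% to 5.3% without treatment and 5.4% to 5.6% with it.

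**Step 4: a weaker treatment effect.** Factor HR 2.0, prevalence 50%:

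| Treatment HR | Estimate, alone | Estimate, with treatment | Gain (points) |
|---|---|---|---|
| 0.4 | 1.84 | 2.03 | 9.8 |
| 0.5 | 1.91 | 2.04 | 6.1 |
| 0.6 | 1.95 | 2.04 | 3.4 |
| 0.8 | 2.00 | 2.04 | 0.2 |

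**Step 5: would treatment reach the multivariable model?** If treatment were screened like any other factor, its chance of passing two-sided p<0.05 at HR 0.4 with 42 events is Φ(2.969 − 1.960) = Φ(1.009) ≈ 84%.

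**The case against.** A reader might infer more from this than the documents support.

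- **That the plan loses 9 to 10 points of power in general.** It does not follow. That is near the maximum, and it needs a factor hazard ratio that the documents do not give.
- **That treatment is a known strong determinant of PFS here.** The 0.4 is the difference the cohorts are powered to detect. Section 2.4 reports regorafenib PFS hazard ratios of 0.493 in colorectal cancer and 0.27 in GIST. The Synopsis speaks of limited activity of this drug class in liposarcoma, while Section 2.5 is more favourable. The loss shrinks quickly as the effect weakens.
- **That treatment is excluded from the multivariable model.** The text is silent. If treatment is one of the screened factors, Step 5 suggests it would usually enter, leaving mainly the loss at the screen.
- **That adjustment is free of any effect on false positives.** The simulation shows a slightly higher rate, still near 5%.
- **That the unadjusted hazard ratios are invalid.** With factor and treatment independent, they estimate a marginal association. Much of the gap is non-collapsibility: adjusted and unadjusted models target different quantities.

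Three further points stand. Stratified randomization limits imbalance between arms on performance status and prior lines, and the simulation did not model it; attenuation does not depend on imbalance, but the exact gain for those two factors was not computed. The predictive models already fit factor and treatment together, although with an interaction the factor's main effect refers to one arm. Prognostic analysis is not among the objectives in Sections 1.1 to 1.3 and drives no decision rule.

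What survives is that the screening model omits treatment by construction. At the plan's own design effect, this costs power and shrinks estimates for factors of moderate size.

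**Conclusion.** The point holds as a minor improvement to a supporting analysis. At treatment HR 0.4, a true factor hazard ratio of 2.0 is estimated at about 1.84 and one of 2.5 at about 2.25. The chance of passing the gate falls by about 9 to 10 points for a binary factor of hazard ratio 2 to 2.5 with prevalence 1/3 to 1/2. At those prevalences the loss is about 4 to 5 points at factor hazard ratio 1.5 and 2 to 3 at 4. For factors of hazard ratio 2 to 2.5 it is about 3 points or less once the treatment hazard ratio is 0.6 or weaker. The factor hazard ratio is an assumption throughout, and so is the prevalence apart from the performance-status ceiling. Omission from the multivariable model is a gap in the text, not a stated choice. The primary stratified log-rank test and its 42 events are not affected.

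**What to change.** Replace the prognostic-factor sentence in Section 12.2 with: *Each prognostic factor is tested in a Cox model that also contains (or is stratified by) randomized treatment, and treatment is kept in the multivariable model regardless of p-value.*

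Keeping the two stratification factors in the multivariable model as well is optional; with 42 events it adds little, and that model was not simulated here.

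The cost is one sentence and no new data, since treatment assignment is held for every patient. Section 3.1 records enrollment to both cohorts as complete by amendment 5, and the documents do not say whether this analysis has been run. If it has, report the treatment-adjusted models as a labelled additional analysis beside the planned ones.
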